### 9.4.3 Safety Analyses

All safety analyses will be based on the safety analysis population according to the treatment assigned at randomization. A summary of key safety analyses is provided in [Table 8](#) below.

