## OBJECTIVES AND ENDPOINTS

Objectives	Endpoints
Primary	

Assess the effect of RG7774 on the severity of DR.

Evaluate the safety and tolerability of RG7774.

	

Proportion of participants with <math>\geq 2</math> step improvement in the Early Treatment Diabetic Retinopathy Study (ETDRS) DR severity score (DRSS) from baseline at Week 36 measured in the study eye.

Frequency and severity of adverse events.

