## **6.2 PREPARATION/HANDLING/STORAGE/ACCOUNTABILITY**

Study treatment packaging will be overseen by the Sponsor clinical trial supplies department and bear a label with the identification required by local law, the protocol number, drug identification and dosage.

The packaging and labeling of the study treatment will be in accordance with Sponsor standard and local regulations.

The investigational site will acknowledge receipt of IMPs and confirm the shipment condition and content. Any damaged shipments will be replaced.

Upon arrival of the IMPs at the site, site personnel will complete the following:

- Check the IMPs for damage.
- Verify proper identity, quantity, integrity of seals and temperature conditions.
- Report any deviations or product complaints to the Study Monitor upon discovery.

The qualified individual responsible for dispensing the study treatment will prepare the correct dose according to the randomization/treatment assignment schedule and the Pharmacy Manual.

The Investigator or delegate must confirm that appropriate temperature conditions have been maintained during transit for all study treatment received and any discrepancies are reported and resolved before use of the study treatment.

Only participants randomized in the study may receive study treatment and only authorized site staff may supply study treatment. All study treatments must be stored in a secure, environmentally controlled, and monitored (manual or automated) area in accordance with the labeled storage conditions with access limited to the Investigator and authorized site staff.

The Investigator is responsible for study treatment accountability, reconciliation, and record maintenance (i.e., receipt, reconciliation and final disposition records).

IMPs will either be disposed of at the study site according to the study site's institutional standard operating procedure or returned to the Sponsor with the appropriate

documentation. The site's method of IMP destruction must be agreed upon by the Sponsor. Local or institutional regulations may require immediate destruction of used IMP for safety reasons. The site must obtain written authorization from the Sponsor before any IMP is destroyed, and IMP destruction must be documented on the appropriate form.

Further guidance and information for the final disposition of unused study treatment are provided in the Pharmacy Manual.

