### **6.4                    TREATMENT COMPLIANCE**

The qualified individual responsible for dispensing the study treatment will prepare the correct dose according to the randomization schedule. This individual will write the date dispensed and participant number on the study treatment bottle label and on the Drug Accountability Record. This individual will also record the medication number received by each participant during the study.

For drug accountability and assessment of compliance by the site, participants are requested to bring back the bottles at every site visit.

In order to increase treatment compliance, the sites are encouraged to offer the participants the option to use a Patient Engagement Mobile Application (PEMA; see Appendix 1, Section 2.1.6). PEMA is an optional service that participants can use to remind them of activities or tasks relevant to the study such as when to take their study treatment or attend clinical site visits. The application also provides study information and any study related supportive instructions. Reminders are delivered to the

participants via push notifications to encourage them to continue their participation and comply with the study.

The study site will assess adherence of the participants to the treatment at every site visit and at every phone call, as specified in the provided script (see Study Procedures Manual). Whenever a participant is, under the opinion of the investigator, not expected to comply with the treatment, the investigator is requested to encourage the study participants and to monitor closely in future visits their adherence.

No diaries will be provided as part of this study.

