**Table 6 Analysis Populations**

Population	Description
Intent-to-treat	The Intent-to-Treat (ITT) population is defined as all participants who give informed consent, are randomized, and receive at least one dose of study treatment (active or placebo). For the ITT population, data will be analyzed according to the treatment participants were randomized to. The ITT population is the primary population of interest.
Safety	The Safety population is defined as all participants who give informed consent, receive at least one dose of study medication (active or placebo) and will be grouped according to the actual treatment received. The Safety population will be used for the analyses of all safety endpoints.
Efficacy	The ITT population will be used for the analyses of all efficacy endpoints.
Pharmacokinetic	All participants in the safety population who have data from at least one post-dose sample will be included in the PK analysis population. Participants will be excluded from the PK analysis population if they significantly violate the inclusion or exclusion criteria, deviate significantly from the protocol, or if data are unavailable or incomplete which may influence the PK analysis. Excluded cases will be documented together with the reason for exclusion. All decisions on exclusions from the analysis will be made prior to database closure.

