- Drug misuse that qualifies as an overdose: Enter the AE term. Check the "Intentional overdose" and "Drug misuse" boxes.

In addition, all special situations associated with RG7774 and placebo regardless of whether they result in an AE, should be recorded on the Adverse Event eCRF and should be recorded as described below:

- Accidental overdose: Enter the drug name and "accidental overdose" as the event term. Check the "Accidental overdose" and "Medication error" boxes.
- Intentional overdose: Enter the drug name and "intentional overdose" as the event term. Check the "Intentional overdose" box. If drug abuse is suspected, check the "Drug abuse" box. If drug abuse is not suspected, check the "Drug misuse" box.
- Medication error that does not qualify as an overdose: Enter the name of the drug administered and a description of the error (e.g., wrong dose administered, wrong dosing schedule, incorrect route of administration, wrong drug, expired drug administered) as the event term. Check the "Medication error" box.
- Medication error that qualifies as an overdose: Enter the drug name and "accidental overdose" as the event term. Check the "Accidental overdose" and "Medication error" boxes. Enter a description of the error in the additional case details.
- Intercepted medication error: Enter the drug name and "intercepted medication error" as the event term. Check the "Medication error" box. Enter a description of the error in the additional case details.
- Drug abuse that does not qualify as an overdose: Enter the drug name and "drug abuse" as the event term. Check the "Drug abuse" box.
- Drug abuse that qualifies as an overdose: Enter the drug name and "intentional overdose" as the event term. Check the "Intentional overdose" and "Drug abuse" boxes.
- Drug misuse that does not qualify as an overdose: Enter the drug name and "drug misuse" as the event term. Check the "Drug misuse" box.
- Drug misuse that qualifies as an overdose: Enter the drug name and "intentional overdose" as the event term. Check the "Intentional overdose" and "Drug misuse" boxes.
- Drug administered to someone other than the participant: Enter the drug name and "patient supplied drug to third party" as the event term. Check the "Drug misuse" box.

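### Section 9.4.3 groups the Safety population by assigned treatment, while Table 6 groups it by treatment received, and adverse events are a primary endpoint

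*Combined protocol and SAP*

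**What the plan says.** Table 6 (Section 9.3) sets out two populations that matter here.

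- **Safety.** Its members are those who "receive at least one dose of study medication (active or placebo) and will be grouped according to the actual treatment received". On scope, the table adds: "The Safety population will be used for the analyses of all safety endpoints".
- **Intent-to-treat.** Its members are participants who consented, were randomized and took at least one dose. For these, "For the ITT population, data will be analyzed according to the treatment participants were randomized to".

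Section 9.4.3 then gives the rule for the safety analyses: "All safety analyses will be based on the safety analysis population according to the treatment assigned at randomization".

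Table 8, which lists the safety methods, names no grouping rule. The synopsis and Table 3 both list "Frequency and severity of adverse events" among the primary endpoints.

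**The concern.** The two sections give opposite grouping rules for the same population and the same set of analyses. Both rules can be followed only if every participant receives exactly what was assigned. If one does not, a programmer working from Table 6 and another working from Section 9.4.3 could produce different primary adverse event tables from the same database.

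Under Section 9.4.3, a participant assigned placebo who was given active drug would have any adverse events counted against placebo. The Section 9.4.3 wording also removes the reason for an as-treated Safety grouping, because it reproduces the grouping that Table 6 already assigns to the ITT population.

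**Working it through.** **Step 1: the two rules side by side.**

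| | Population | Scope | Grouping |
|---|---|---|---|
| Table 6 | Safety | all safety endpoints | treatment received |
| Section 9.4.3 | Safety | all safety analyses | treatment assigned |

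Population and scope match, and the grouping conflicts. Neither statement is limited to a subset of analyses, and neither comes from the amendment summary.

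**Step 2: what Section 9.4.3 does to the Safety population.** Section 6.2 says: "Only participants randomized in the study may receive study treatment". If that is followed, the dosed participants are the randomized and dosed participants, which is Table 6's ITT population, already analysed as randomized. Section 9.4.3 therefore makes the safety groups identical to the ITT groups. If someone were dosed without being randomized, in breach of Section 6.2, Table 6 would give that person a group and Section 9.4.3 would not. The Safety population still determines who can enter the PK population. Only its as-treated grouping is undone.

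**Step 3: scale if a misallocation occurs.** The plan gives no misdosing rate and no figure to reproduce on this point. The only input from the documents is the group size of 45 (Section 9.2). It is consistent with 40 completers and 10% loss: 40/0.9 = 44.4, rounded up to 45. The assumption is that, as randomized, x participants out of 45 have a given event in each of the two affected arms. Moving from assigned to received treatment takes one person out of one arm (45 to 44) and adds that person to the other (45 to 46).

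*The moved participant had the event:*
- Losing arm falls by x/45 − (x−1)/44 = (45−x)/1980.
- Gaining arm rises by (x+1)/46 − x/45 = (45−x)/2070.
- The arms move in opposite directions, so the difference between them shifts by the sum.

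*The moved participant did not have the event:*
- Losing arm rises by x/44 − x/45 = x/1980.
- Gaining arm falls by x/45 − x/46 = x/2070.

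Shifts in percentage points (losing arm + gaining arm = difference):

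| x | Had the event | Did not have the event |
|---|---|---|
| 1 | 2.22 + 2.13 = 4.35 | below 0.1 per arm |
| 10 | 1.77 + 1.69 = 3.46 | 0.51 + 0.48 = 0.99 |
| 22 | 1.16 + 1.11 = 2.27 | 1.11 + 1.06 = 2.17 |
| 44 | below 0.1 per arm | 2.22 + 2.13 = 4.35 |

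The shift is zero in some cases, for example when x = 0 and the moved participant had no event. Exchanging one participant with the event and one without between two arms shifts each arm by 1/45 = 2.22 points and the difference by 2/45 = 4.44 points, whatever x is. Exchanging two participants with the same event status shifts nothing.

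**Step 4: a mix-up between the two active doses.** Take 10/45 in every arm and one participant with the event who was assigned 200 mg and took 30 mg. Regrouping changes 30 mg versus placebo by 11/46 − 10/45 = +1.69 points and 200 mg versus placebo by 9/44 − 10/45 = −1.77 points. A dose mix-up can therefore move both placebo contrasts as well as the contrast between doses.

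**The case against.** The strongest case concerns weight. Treatment is assigned centrally through IxRS and medication numbers are recorded, so misallocation between arms may never happen, and then the two rules give the same tables. Appendix 2, Section 5.2 does list "wrong dose administered, wrong dosing schedule, incorrect route of administration, wrong drug, expired drug administered" as examples of medication errors, but these are generic recording instructions. Most such events would not change a participant's arm. No safety test is planned and efficacy is untouched. Section 9.4.2 also promises a separate document with full analysis details, which was not supplied and might settle the rule.

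The point about frequency stands: the expected effect is unknown and may be nil, and the figures above show scale only. The point about the separate document does not remove the problem. The promise sits in the efficacy section, and whichever rule that document adopts will contradict one of the two protocol statements. Rarity limits the likely size of the effect but leaves the rule for a primary endpoint contradictory.

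**Conclusion.** The concern holds. Sections 9.3 and 9.4.3 contradict each other on how the Safety population is grouped, and nothing in the supplied documents reconciles them. The contradiction is certain; its numerical effect is not. With 45 per arm and equal event counts in the two affected arms, one misallocated participant shifts the difference between those arms by somewhere from zero to about 4.3 points. The shift can grow if several participants are misallocated, but the documents give no basis for any particular number. No formal test depends on the choice. The point should be corrected because it concerns a primary endpoint, and because Section 9.4.3 as written counts a misdosed participant's events in an arm whose treatment that person did not take.

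**What to change.** In Section 9.4.3, replace the closing reference to assigned treatment with grouping by treatment actually received, so that the sentence agrees with Table 6. The cost is one phrase, with no new data and no change to the sample size or any test.

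As an optional addition, state before unmasking how a participant who received more than one treatment is classified, and list such participants separately. This takes one sentence. Section 6.4 already provides the main source: "This individual will also record the medication number received by each participant during the study", together with dispensing dates. No diaries are kept, so these records show what was dispensed rather than daily intake. Returned containers (Sections 6.2.1 and 6.4), dosing in the clinic on visit days and scheduled PK samples (Table 1 notes) can support the classification.

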**Table 8 Safety Statistical Analysis Methods**

Endpoint	Statistical Analysis Methods
Adverse events	The original terms recorded on the eCRF by the Investigator for adverse events will be coded by the Sponsor. Adverse events will be summarized by mapped term and appropriate thesaurus level.
Ocular investigations and Clinical laboratory tests	All clinical laboratory data will be stored on the database in the units in which they were reported. Laboratory test values will be presented in International System of Units (SI units; Système International d'Unités) by individual listings with flagging of abnormal results. Summary and change from baseline in laboratory parameters of clinical significance will be provided.
Vital signs	Vital signs data will be presented by individual listings with flagging of values outside the normal ranges and flagging of abnormalities. In addition, tabular summaries will be used, as appropriate.
ECG data analysis	ECG data will be presented by individual listings. In addition, tabular summaries will be used for raw values as well as changes from baseline.
Concomitant medications	The original terms recorded on the participants' eCRF by the Investigator for concomitant medications will be standardized by the Sponsor by utilizing a mapped term and appropriate drug dictionary level. Concomitant medications will be presented in summary tables and listings.

**9.4.4 Pharmacokinetic Analyses**

Analyses will be carried out on the PK analysis population. All pharmacokinetic parameters will be presented by listings and descriptive summary statistics (mean, standard deviation, coefficient of variation, median, minimum, and maximum) separately by group or cohorts.

A nonlinear mixed effects modeling approach will be used to analyze the sparse sampling dose-concentration-time data of RG7774 (and its metabolite(s) as appropriate) collected in this study. Those data collected may be pooled with data collected in previous phase I studies as appropriate to build the pharmacokinetic model. Population and individual primary pharmacokinetic parameters (e.g., apparent clearances and volumes) will be estimated and the influence of various covariates on these parameters will be investigated. Secondary PK parameters such as AUC and  $C_{max}$  will be derived from the individual post-hoc predictions. Graphical exploration of the relationship between RG7774 concentrations and DRSS, other selected clinical endpoints, biomarkers and safety endpoints may be performed. If indicated by such exploration, more formal analyses of the PK/PD relationship using non-linear mixed effects modelling method will be undertaken.

Details of the modelling analyses will be described in a Modelling and Simulation Analysis Plan. The results of this analysis will be reported in a separate document from the Clinical Study Report.

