**Table 1 Schedule of Activities – Main Table (cont.)**

13. *One PK sample to be collected at all visits prior to study treatment administration. At visits Day 1, Day 28, and Day 252 two additional post-dose samples may be collected optionally. The two samples should be obtained at 1-3 hours, and 3-5 hours post-dose, respectively. Timing between the two post-dose samples should be approximately 2 hours.*
14. [REDACTED]
15. *Study eye only.*
16. qCSF to be performed only if the site has the capabilities to perform this assessment.
17. *Optional Visual Field assessments should be performed in study eye only when the site has the capabilities to perform this assessment.*
- 18a. Only one FFA modality will be performed in each patient: *ultra-widfield-FFA* will be performed preferentially, if the site has the capabilities to perform this assessment. If not available, 7F-FFA will be performed.
- 18b. Fluorescein Angiography assessments not to be done more often than every *12 weeks*.
19. Study medication will be administered to participants directly in the study clinic on the day of site visit. The participant has to avoid taking medication before going to the site on the day of site visit.
20. Adverse event collection will be done throughout the full length of the study.
21. Patient Engagement App (PEMA) will be used at discretion of the participant, if applicable, throughout the full length of the study (no time restriction on Day 1).

**Table 2 Schedule of Activities – Reduced Assessments as from the Time of Rescue Treatment and up to and including Week 36**

	Assessments in case of rescue treatment
Previous and Concomitant Treatments / Medications	x
Physical Examination	x
Vital Signs	x
Triplicate ECG-12 lead	x
Hematology	x
Blood Chemistry	x
Coagulation	x
Lipids	x
HbA1c	x
Urinalysis	x
TSH	x
C-SSRS (Form "Since Last Visit")	x
PK Sample	x
IOP	x
BCVA	x
Slit Lamp	x
Indirect Ophthalmoscopy	x
Fundus Photography (7F-FP)	x
SD-OCT	x
Dispensing and/or return of study medication	x
RG7774 / placebo	x
Adverse Events	x
Optional Aqueous Humor sample 	x

Optional aqueous humor sample collection to be performed prior to the intravitreal rescue treatment in participants who give additional consent.

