## **8.5 PHARMACOKINETICS**

Blood samples for pharmacokinetic determination of plasma concentrations of RG7774 (and its metabolite[s] as appropriate) will be collected as specified in the Schedule of Assessments Table.

The actual date and time of the PK blood sampling needs to be precisely entered into the corresponding eCRF section.

Plasma concentrations of RG7774 will be measured by a specific and validated LC-MS/MS method. Plasma concentrations of RG7774-derived metabolite(s) may be measured (as appropriate) for exploratory metabolite(s) quantification purposes, with the use of non-validated LC-MS/MS method(s). Any residual material from blood PK samples may be used for additional exploratory biomarker profiling, identification, assay development purposes, and assay validation or compound-related assays after the mentioned intended use. All PK samples will be destroyed at the latest 5 years after the final clinical study report (CSR). Details on sampling procedures, sample storage and shipment are given in the Sample Handling Manual.

Additional PK sampling at unscheduled visits is allowed at the discretion of the investigator for safety purposes (see Section 8.4).

Study treatment concentration information that may unmask the study, will not be reported to investigative sites or masked personnel until the study has been unmasked.

Any changes in the timing or addition of time-points for any planned study assessments must be documented and approved by the relevant study team member and then,

archived in the Sponsor and site study files, but this will not constitute a protocol amendment. The IRB/IEC will be informed of any safety issues that require alteration of the safety monitoring scheme or amendment of the ICF.

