**Table 7 Efficacy Statistical Analysis Methods (cont.)**

Change from baseline in participants with DME at baseline in:
 
 
• BCVA (as measured on the ETDRS chart at a starting distance of 4 meters) at post-baseline visits.
 
• Central subfield thickness on SD-OCT at post-baseline visits.
 
 
Proportion of participants with absence of signs of DME and normalized CST over time
	
Analysis of variance model for longitudinal data taking into account repeated measures within each participant.

Change from baseline in Contrast Sensitivity at post-baseline visits in the study eye (Pelli-Robson, qCSF) or in both eyes (qCSF).
	
Analysis of variance model for longitudinal data taking into account repeated measures within each participant.

Change from baseline in LLVA at Week 36 visit in the study eye.
	
Analysis of variance model for longitudinal data taking into account repeated measures within each participant.

Absolute change from baseline in mean threshold and in point-by-point Standard Automated Perimetry at post-baseline visits.
	
Analysis of variance model for longitudinal data taking into account repeated measures within each participant.

PK parameters of RG7774 (and its metabolite(s) as appropriate) in plasma and (if applicable) in optional aqueous humor.
	
Descriptive summaries of the PK parameters (e.g., <math>C_{max}</math>, AUC, etc.)

Change from baseline in blood levels of HbA1c.
	
Descriptive summaries by treatment group and visit

Performance of the advanced analytic tools
	
Analysis of the exploratory efficacy endpoints

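### Individual Cmax is summarised from post-hoc predictions although only pre-dose PK samples are mandatory, so the reported SD and CV of Cmax can be biased low

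*Combined protocol and SAP*

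**What the plan says.** Section 9.4.4 plans a nonlinear mixed effects model for sparse data and says that secondary parameters such as AUC and Cmax "will be derived from the individual post-hoc predictions". The same section says: "All pharmacokinetic parameters will be presented by listings and descriptive summary statistics". The statistics listed are "descriptive summary statistics (mean, standard deviation, coefficient of variation, median, minimum, and maximum) separately by group or cohorts". Table 7 gives the method for the PK endpoint as "Descriptive summaries of the PK parameters", with Cmax and AUC as examples.

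Footnote 13 of Table 1 sets the sampling: "One PK sample to be collected at all visits prior to study treatment administration". On Day 1, Day 28 and Day 252, "two additional post-dose samples may be collected optionally", at 1–3 h and 3–5 h. The rationale for version 5 lists the move of the post-dose samples from required to optional.

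Table 6 admits to the PK population anyone in the safety population with at least one post-dose sample, without defining that term. Section 9.4.4 allows pooling with Phase I data as an option and leaves modelling detail to a separate Modelling and Simulation Analysis Plan. It also mentions an optional graphical look at concentrations against efficacy and safety endpoints. Table 3 lists PK and exposure-response/safety as exploratory.

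**The concern.** A post-hoc (empirical Bayes) prediction is a compromise between a person's own data and the population value. Where the person's data say little about a parameter, the prediction sits near the population value. The spread of such predictions is then not the between-subject spread.

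A participant who declines the optional samples has a Day 1 sample taken before any drug, and four steady-state troughs (Weeks 4, 12, 24 and 36). Troughs inform clearance, and hence AUC, reasonably well. They say little about that person's absorption rate and volume, which shape the peak. The rationale for version 5 lists no matching change to Section 9.4.4, and the section names no shrinkage report, minimum uptake or other source for SD and CV.

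At stake is the description of how variable peak exposure is in patients. The minimum and maximum are compressed along with the SD. Table 4 gives a monkey Cmax margin of more than 3 at 200 mg (7,850/2,150 = 3.65), so the upper spread of Cmax is useful to know. Any relation of Cmax to response or safety within one dose arm would also be blurred.

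**Working it through.** The documents state no SD or CV of Cmax, no between-subject variance, no residual error and no expected uptake. There is no plan figure to reproduce, so the planned estimator was simulated.

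**Inputs from the documents (Table 4, 200 mg)**
- Steady-state Cmax 2,150 ng/mL and AUCtau 24,000 h·ng/mL.
- CL/F = 200 mg / 24,000 h·ng/mL = 8.33 L/h.
- Average concentration = 24,000/24 = 1,000 ng/mL, so Cmax/Cavg = 2.15.
- Sampling from footnote 13: four troughs, with or without post-dose pairs (taken as 2 h and 4 h) at Weeks 4 and 36. The optional Day 1 pair was not included.

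**Assumptions (not in the documents)**
- One compartment; absorption rate 0.5–2 per hour; V/F solved so that the typical Cmax is 2,150.
- Between-subject SD on the log scale: CL/F 0.2–0.4, V/F 0.15–0.4, absorption rate 0.3–0.6. CL/F–V/F correlation 0–0.8. Residual SD 0.2–0.4.
- Population parameters known, troughs at exactly 24 h, no variation between occasions.
- 300–400 simulated participants per scenario.

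**Principle.** Under a correct model, Var(true Cmax) = Var(posterior mean) + mean posterior variance. The second term is never negative, so the SD of individual predictions is at most the true SD, and it falls as individual data become less informative. The usual post-hoc estimate is the posterior mode, which minimises Σ[(log y − log C(t))/σ]² + η′Ω⁻¹η; the simulation used this estimate.

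**Results over all scenarios: SD of post-hoc values divided by true SD**

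| Data | Cmax SD ratio | Correlation with true Cmax |
|---|---|---|
| Troughs only | 0.18–0.78 | 0.15–0.80 |
| Pairs in 25% (subset of scenarios) | 0.51–0.83 | not summarised |
| Pairs in 50% | 0.51–0.86 | not summarised |
| Pairs in 100% | 0.69–0.96 | 0.64–0.95 |

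For AUC with troughs only, the SD ratio was 0.61–0.98 and the correlation 0.56–0.96. The low end arises where clearance varies little and volume varies a lot.

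**Selected scenarios (absorption rate 1 per hour, residual SD 0.25)**

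| SD of CL/F, V/F, absorption | CL/F–V/F corr. | True → post-hoc CV of Cmax, troughs only | Cmax SD ratio at 0 / 25 / 50 / 100% uptake |
|---|---|---|---|
| 0.3, 0.3, 0.6 | 0 | 25% → 5% | 0.21 / 0.51 / 0.60 / 0.83 |
| 0.4, 0.4, 0.5 | 0.5 | 38% → 13% | 0.35 / 0.58 / 0.73 / 0.96 |
| 0.4, 0.2, 0.5 | 0.8 | 28% → 22% | 0.78 / 0.83 / 0.86 / 0.93 |

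**Contrast across doses.** Table 4 predicts Cmax of 352 and 2,150 ng/mL, a log gap of ln(2,150/352) = 1.81. With equal arms the between-arm variance is (1.81/2)² = 0.819. Take a low-information case: within-arm correlation 0.15, SD ratio 0.34, true within-arm log SD s = 0.3 or 0.4.
- s = 0.3: covariance 0.819 + 0.15×0.34×0.09 = 0.824; true variance 0.819 + 0.09 = 0.909; post-hoc variance 0.819 + 0.34²×0.09 = 0.829. Correlation = 0.824/√(0.909×0.829) = 0.95.
- s = 0.4: covariance 0.827, true variance 0.979, post-hoc variance 0.837. Correlation = 0.827/√(0.979×0.837) = 0.91.

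Pooled over both doses, post-hoc Cmax still ranks participants well. The loss is within arms.

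**The case against.** Table 6 may already exclude the affected participants. Footnote 13 uses the term post-dose for the 1–3 h and 3–5 h samples and sets them against samples taken before dosing. On that reading anyone with troughs only is outside the PK population, and the bias shrinks to what remains with post-dose data. This is a fair reading, but Table 6 does not settle it, and it would remove those participants from the AUC summary as well.

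Pooling with Phase I data and the separate modelling plan might also be thought to cover the point. Pooling is optional. It informs typical values and variances, not the peak of a person who has only troughs. Phase I multiple dosing was also in fasted healthy volunteers, whereas dosing here is preferably with breakfast. The modelling plan may well report shrinkage, but Section 9.4.4 already commits to the post-hoc derivation and to the statistics computed from it.

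The size is uncertain, and this stands. Uptake may be good, and participants enrolled before version 5 may have post-dose samples.

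Two stronger readings are tempting and are not supported:
- A reader might infer that Cmax cannot be related to safety at all. The gap between the two doses argues against this. Section 9.4.4 also names concentrations, not Cmax, for a look that is itself optional.
- A reader might infer that troughs cannot be interpreted because the time of the previous home dose goes unrecorded. Section 8.5 says "The actual date and time of the PK blood sampling needs to be precisely entered", and Section 6.4 says "No diaries will be provided as part of this study". But Section 9.4.4 refers to dose-concentration-time data, and the eCRF and Sample Handling Manual are not available here, so a missing field is not shown.

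**Conclusion.** The point holds conditionally. If on-treatment troughs count as post-dose samples in Table 6, Section 9.4.4 commits to a statistic that is biased low for participants without the optional samples. The direction was the same in every scenario. The size rests on a one-compartment model, assumed variances and unknown uptake: the Cmax SD is roughly 0.2 to 0.8 of the truth with troughs only, and about 0.7 to 0.96 with full uptake. AUC is usually less affected, though not in every scenario. Within-arm relations of Cmax with response or safety are weakened, while contrasts across the two doses are largely preserved. The primary efficacy analysis is untouched and the PK endpoint is exploratory, so this is a correction to make rather than a threat to the trial's conclusions.

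**What to change.** In Section 9.4.4, do one of the following:
1. Take the between-subject SD and CV of Cmax and AUC from the model's estimated variances, by simulation from the final model. This is the better choice for SD and CV, because some shrinkage remains even with full uptake.
2. Summarise individual Cmax only for participants with at least one sample 1–5 h after dosing, and say how many there are.

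With either choice:
- Report shrinkage for clearance, volume and absorption rate, and the uptake of the optional samples by arm.
- For participants with troughs only, use AUC or pre-dose concentration, not Cmax, in any within-arm exposure-response or exposure-safety analysis.
- Define the post-dose sample in Table 6, stating whether an on-treatment trough counts.

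The cost is wording in Section 9.4.4, Table 6 and the modelling plan; no new sampling is needed. The downside of the second choice is that individual Cmax is reported for fewer participants, who will be those who agreed to extra sampling.
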